8.1 Primary outcome measure: surgical success rate

The surgical success rate is defined as the proportion of successfully operative subjects in the experimental group or the control group.

Surgery conversion in this study means a robotic surgery has to be converted to a

laparoscopic surgery. Usually there are 3 kinds of reasons: active conversion, passive conversion and malfunction of the endoscopic instrument control system.

(1) Active conversion:

During the surgery, surgeons may encounter some situations that make them impossible to keep the operation going such as severe adhesion, anatomical variation or failing to expose the surgical site. Or when surgeons are dissociating the tissue, they have difficulties to find certain important vascular structure and to make a normal anatomy of the clearance. At this point, surgeons initiatively decide to convert to a laparoscopic surgery.

(2) Passive conversion:

During the surgery, some unexpected accidents happen and surgeons have to convert to laparoscopic surgery. Usually these accidents include injury of tissues and organs, unstoppable bleeding, and difficult suture using the surgical robot. Passive conversion is related to surgical techniques of the surgeons. With the experience accumulating and the operative skill improving of surgeons, the passive conversion rate will decrease significantly.

(3) Malfunction of the endoscopic instrument control system:

Serious malfunction of the test product may occur during the surgery (such as strong interference between the console and the operative part, the operative arm dysfunction and can't be repaired by resetting, surgical instrument can't loosen the tissue, etc.) The operation is unable to continue, so surgeons have to convert to laparoscopic surgery. Usually the malfunction is caused by unreasonable design, unqualified instruments or inappropriate operation of the product arms. It indicates the deficiency of the test product.

Notes:

1) Surgical success is defined as the successful completion of all surgical operations through the experimental products or the control products.

2) Surgical failure is defined as the unaccomplishable surgical operations using the experimental or control products as planned. The reason includes passive conversion and malfunction of the products. Noticeably, active conversion does not mean a surgical failure.

8.2 Secondary outcome measures:

(1) The breakage rate of gallbladder:

The breakage rate of gallbladder is defined as the proportion of the subjects in the experimental group or the control group with specimen breakage.

(2) Comprehensive Complication Index (CCI)

CCI is calculated using online tools provided by <http://cci.assessurgery.com>. Based on the Clavien-Dindo complications grade system (appendix.1), all complications and adverse events after surgical intervention are taken into consideration. The overall incidence is measured on a scale ranging from 0 (no complication) to 100 (death).

(3) Operative time (min)

The length of time from the beginning of the operation after the robot installation to the end of the suture of the incision.

(4) Intraoperative bleeding (L)

The total bleeding volume from the beginning of the operation to the end of the suture of the incision. It can be calculated by measuring the blood volume in the vacuum suction device and weighing the gauze after using them to wipe the bleeding.

(5) Postoperative pain

Postoperative pain is assessed by visual analogue scale (VAS) 24-26 hours after the operation, ranging from 0 (no pain) to 10 (maximum pain).

(6) Time to first flatus (h)

The time from the end of the operation to the subject's first flatus after surgery.

(7) Surgeon's satisfaction

After the operation, surgeons fill a questionnaire to score the flexibility, intuition and stability of the products, as well as their sense of delay and fatigue when using the products. Each question in the score ranges from 1 to 5 points and the total score is 100.

(8) Installation time (min)

The time from the power-on of the products to the end of the connection between trocars and the operative arms.

(9) Hospital stay (days)

The total hospital days of subjects from admission to discharge.

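### Under Note 2 of Section 8.1, conversions caused by device limits short of serious malfunction can be classed as active and leave the failure count of a non-inferiority endpoint

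*Protocol*

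**What the plan says.** Protocol Section 8.1 makes the surgical success rate the primary outcome and defines conversion as a change from robotic to laparoscopic surgery. On the reasons it says: "Usually there are 3 kinds of reasons: active conversion, passive conversion and malfunction of the endoscopic instrument control system".

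- **Active.** The examples are marked adhesions, variant anatomy and "failing to expose the surgical site", and cases where, during dissection, "they have difficulties to find certain important vascular structure and to make a normal anatomy of the clearance". Then "surgeons initiatively decide to convert to a laparoscopic surgery".
- **Passive.** Unexpected events such as organ injury, bleeding that cannot be stopped, and "difficult suture using the surgical robot". The text ties this class to surgeon technique.
- **Malfunction.** Serious malfunction of the system that prevents the operation from continuing. The examples given are not exhaustive.

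Note 1 calls an operation a success when all of it was completed with the assigned system. Note 2 names passive conversion and malfunction as reasons for failure and adds: "Noticeably, active conversion does not mean a surgical failure".

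Sections 1 and 5(6) set the aim as non-inferiority to the control system. Section 2 describes the trial as single-blind. Under Section 8.2(7) the surgeon scores the system after operating with it. Section 7.6 plans 84 subjects per arm.

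**The concern.** Adhesion and anatomical variation are findings in the patient. Failed exposure and failed dissection need not be. Section 10.2(5) shows that grasping, pulling and dissecting the gallbladder are largely done with the system under study, so poor reach, grip or vision could produce exactly these reasons. Section 8.1 has no test that separates the two causes.

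Under Note 2, such a conversion is not a failure. If the test system is worse in this respect, some of its true failures go uncounted, the observed difference moves towards zero, and a false claim of non-inferiority becomes more likely. Anyone who classes the case from the surgeon's account relies on someone who knows the arm, so errors in the label need not be equal between arms.

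**Working it through.** **1. The text, side by side.** Take a conversion because the robot, though working as built, could not expose or dissect well enough.

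| Rule in Section 8.1 | How the case is treated |
|---|---|
| (1) Active | Fits the listed reasons; no patient cause is required |
| (2) Passive | Does not fit well; no accident has happened |
| (3) Malfunction | Does not fit unless the limitation is a serious malfunction |
| Note 2 | Not a failure, because it is active |
| Note 1 | Not a success, because the operation was not completed with the system |

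The gap therefore exists under Note 2 and closes under Note 1.

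**2. Who assigns the class.** Section 8.1 says the surgeon decides to convert. It does not say who classes the case for the endpoint. The surgeon operates and scores the system, so knows the arm. No blinded or independent classifier is named.

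**3. Inputs for the size.** n = 84 per arm (Section 7.6). The protocol gives no margin or expected rates, so every margin, rate and count below is an assumption. No figure in the protocol is disputed.

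**4. Effect on one result.** One relabelled case moves an arm's rate by 1/84 = 1.2 points. With p1 (test) and p2 (control) as success proportions and (l, u) as Wilson 95% limits, the lower Newcombe limit is

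L = (p1 − p2) − √[(p1 − l1)² + (u2 − p2)²]

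- Test 78/84, control 82/84 (6 and 2 conversions, all counted): −0.0476 − √(0.0758² + 0.0173²) = −0.125, that is −12.5 points.
- Test 80/84, control 82/84 (two test-arm cases labelled active): −0.0238 − √(0.0685² + 0.0173²) = −0.094, that is −9.4 points.
- Test 80/84, control 83/84 (one control case also labelled active): −0.0357 − √(0.0685² + 0.0098²) = −0.105, that is −10.5 points.

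With relabelling in the test arm only, the conclusion reverses for margins between about 9.4 and 12.5 points. At 5 or 8 points both analyses fail; at 15 both pass. With the control case relabelled too, there is no reversal at 10 points.

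**5. Effect on the false-claim rate.** Let the test arm be worse by exactly the margin, and let a share q of true failures be labelled active. If q is the same in both arms, the expected observed difference is (1 − q) times the true one. For 15% against 5% and q = 0.5 it is 7.5% − 2.5% = 5 points instead of 10. If only the test arm is relabelled, it is 7.5% − 5% = 2.5 points. The chance of declaring non-inferiority is the sum, over all pairs of failure counts, of the product of the two binomial probabilities for pairs with L above minus the margin.

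| Assumed margin; control failure rate | q | Same share in both arms | Test arm only |
|---|---|---|---|
| 10 points; 5% | 0 | 2.6% | 2.6% |
| 10 points; 5% | 0.25 | 8.5% | 13.6% |
| 10 points; 5% | 0.50 | 25.8% | 46.4% |
| 5 points; 2% | 0 | 1.6% | 1.6% |
| 5 points; 2% | 0.50 | 8.4% | 15.4% |

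The false-claim rate rises even when labelling is the same in both arms.

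**The case against.** The strongest objection is that the bias is conditional. On Note 1 a converted case is never a success, so its label does not matter. That stands: this point arises only if Note 2 prevails. But Note 2 states its intent on active conversion expressly, so that outcome is a real possibility, and resolving the Notes that way would leave the class boundary unrepaired.

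Several stronger readings are tempting, and the documents do not support them:

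- *The surgeon assigns the class.* This is a reasonable inference from "At this point, surgeons initiatively decide to convert to a laparoscopic surgery" and from the absence of a named classifier, but the protocol does not say so.
- *Difficult suturing is the same device limitation, treated inconsistently.* Section 8.1 links passive conversion to surgeon technique, so it offers its own reason for that class.
- *Device-caused conversions in general escape.* Serious malfunctions count as failures, the examples of malfunction are open-ended, and design faults are named among their causes. The gap is limited to shortcomings below that level and to borderline cases.
- *Two labels reverse the trial's conclusion.* This needs a margin in a particular range and relabelling in the test arm only. Nothing in the protocol shows that labelling would favour the test arm.

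It can also be said that an extra sensitivity analysis may sit in the SAP, which is not at hand. That is fair, and its absence is not the finding. The classes and the failure rule are fixed in the protocol, and an SAP would inherit the labels they produce.

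**Conclusion.** The point holds in a limited form. If Note 2 governs, Section 8.1 lets conversions caused by device limits short of serious malfunction leave the failure count, because failed exposure and difficult dissection are active whatever their cause. Failure is then judged in a setting where the surgeon knows the arm and no blinded or independent classification is described.

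If the test device is worse, the direction is towards non-inferiority, with or without unequal labelling. The size cannot be fixed from the protocol. Under the assumptions shown, labelling half of the failures active in both arms raises the false-claim rate from 2.6% to 25.8% (10-point margin) or from 1.6% to 8.4% (5-point margin). The shares relabelled are illustrative; nothing in the document indicates how often it would happen. The change should be made unless the Notes are settled in favour of Note 1, in which case the point falls away.

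**What to change.** Change Section 8.1 for endpoint scoring only. When surgeons convert stays as it is.

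- **(a) Label-free analysis.** Prespecify an analysis of the primary outcome in which every conversion, whatever its reason, counts as non-success in both arms. Report it beside the primary result, and state that a disagreement between the two weakens the non-inferiority claim. It need not be a joint condition for the claim, since that could cost power and the basis of 84 per arm is not shown.
- **(b) Classes by cause.** For scoring, limit active conversion to documented patient findings such as adhesion or anatomical variation. Score failed exposure or dissection without such a finding as failure. Record the reason in the CRF at the end of the operation. This narrows the room for judgement but does not blind the label; only (a) is independent of it.

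Cost: protocol and CRF wording and one further analysis. The reported success rate may be slightly lower in both arms, which can slightly reduce power. If the Notes are settled in favour of Note 1, the primary analysis already does what (a) asks.

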Clinical Trial Protocol

TITLE: Prospective, Multicenter, Randomized, Single-blind, Parallel-controlled Clinical Trial Protocol for the Safety and Efficacy of Clinical Applications of the Endoscopic Instrument Control System

PROTOCOL ID: SDWG-NST600S-CT

DOCUMENT TYPE: Study protocol

DATE: 2019-09-01

SPONSOR: The Third Xiangya Hospital of Central South University

COLLABORATOR: The Affiliated Hospital of Qingdao University

Study protocol

1. Study purpose

To evaluate the safety and efficacy of the MicroHand S endoscopic instrument control system by using it in clinical treatment for the participants. Statistical analysis is conducted to determine whether the efficacy of the test product is non-inferior to that of the control product and to observe the incidence of organ and vascular injury related to the test product. Thus, to verify the safety and efficacy of the MicroHand S endoscopic instrument control system developed by WEGO Surgical Robot Co., Ltd in clinical application.

2. Content

This clinical trial is a prospective, multicenter, randomized, single-blind, parallel-controlled study. The instrument used in the experimental group is the endoscopic surgical robotic system developed by WEGO Surgical Robot Co., Ltd., and the instrument used in the control group is the endoscopic surgical robotic system developed by Intuitive Surgical.

Before patients are enrolled in this clinical study, the researchers will do a detailed screening of the subjects based on the inclusion and exclusion criteria to determine if the patients are appropriate for the clinical study. Patients who meet the conditions of the study will be required to sign an informed consent form. Then they will be randomly assigned to the test group or the control group. The surgical robot system will be used for treatment in both groups to evaluate the primary and secondary outcome measures and to observe the incidence of organ and vascular injury.

Finally, we evaluate the safety and efficacy of the test product through the comparison of the data obtained from the test group and the control group during the treatment.

3. Background

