5. Study Methods

- (1) This study uses a multicenter, randomized, single-blind, parallel-controlled method to observe the efficacy and safety of the MicroHand S endoscopic instrument control system in clinical application.
- (2) The subjects' vital signs are recorded before the start of this study, which include blood routine, liver and kidney function, electrolytes, coagulation function, electrocardiogram, urine/blood pregnancy test (female) and related imaging examination. Preoperative combined medications are also recorded.
- (3) Qualified subjects are divided into the experimental group and the control group by randomized number given in an envelope. Both the endoscopic instrument control systems in two groups are examined before the test. After anesthesia, the endoscopic instrument control system is placed in an appropriate position. Then we connect the wires and power up the system. According to the requirements of the surgery, the operative arms are placed and slowly pushed through the Trocars of the abdominal wall. The surgeons start to perform the operation.
- (4) Surgical success rate, intraoperative blood loss, operative time, and installation time are recorded, as well as whether adjacent organs and blood vessels are injured due to the malfunction of the test system. The breakage rate of gallbladders is calculated. Surgeons need to fill the satisfaction questionnaire after the surgery.
- (5) Subjects take a test in 24 ± 2 hours after surgery using visual analogue scale (VAS) to evaluate the pain score. Postoperative blood routine examination, liver and kidney function, and electrolyte examination are performed. Time to first flatus, postoperative complications and hospital stay are recorded. Postoperative combined medications are also recorded. Adverse events and severe adverse events are assessed separately in 30 ± 5 days after surgery.
- (6) After the follow-ups of all subjects, the data will be arranged for statistical analysis. Ultimately the data of the two groups will be compared, so as to prove whether the experimental product developed by WEGO Surgical Robot Co., Ltd is non-inferior to the control group.

6. Arms and Interventions

- (1) Experimental group: MicroHand S endoscopic instrument control system
Using the MicroHand S endoscopic instrument control system to treat gallstone or cholecystitis in minimal invasive surgery.

(2) Control group: da Vinci endoscopic instrument control system

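### Section 8.1 gives actively converted operations two incompatible statuses, so the only primary endpoint can be computed in two ways

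*Protocol*

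**What the plan says.** Protocol section 8.1 names one primary outcome: "The surgical success rate is defined as the proportion of successfully operative subjects in the experimental group or the control group". It describes conversion as a change from robotic to laparoscopic surgery and gives three kinds: active, passive, and conversion because of system malfunction.

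- **Active conversion, 8.1(1).** The surgeon meets severe adhesions, variant anatomy, poor exposure or vessels that are hard to identify. "At this point, surgeons initiatively decide to convert to a laparoscopic surgery".
- **Passive conversion, 8.1(2).** An unexpected accident forces the change. "Usually these accidents include injury of tissues and organs, unstoppable bleeding, and difficult suture using the surgical robot".
- **Note 1.** "Surgical success is defined as the successful completion of all surgical operations through the experimental products or the control products".
- **Note 2.** Failure is an operation that cannot be accomplished with the product as planned. "The reason includes passive conversion and malfunction of the products". It ends: "Noticeably, active conversion does not mean a surgical failure".

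Section 1 states the aim, to "determine whether the efficacy of the test product is non-inferior to that of the control product". Section 7.6 sets 84 patients per group. In section 5(4), the list of intraoperative items begins "Surgical success rate, intraoperative blood loss, operative time, and installation time are recorded"; it names neither conversion nor its reason.

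**The concern.** A proportion of successes needs each patient in the group to be either a success or not. Note 1 puts an actively converted patient outside success, and Note 2 puts the same patient outside failure. Two analysts can each follow section 8.1 faithfully and report different rates from the same data.

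The direction of the effect is open. If active conversions are more frequent in the test arm, counting them as successes favours non-inferiority. If they are more frequent in the control arm, counting them as non-successes favours it. If they are balanced, the choice mainly affects precision. A choice made after the counts are known would be post hoc.

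Status also turns on whether the surgeon calls a conversion active or passive. The trial is single-blind, and the surgeon at the console necessarily knows which system is in use.

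**Working it through.** **1. The two Notes applied to one patient.** Take a patient whose surgeon stops the robotic procedure because of severe adhesions and finishes laparoscopically.

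| Rule in section 8.1 | Status of this patient |
|---|---|
| Note 1, definition of success | Not a success: not all of the operation was done through the assigned robot |
| Note 2, general definition of failure | Literally a failure: it could not be done with the robot as planned |
| Note 2, named reasons | Not listed (passive conversion and malfunction are) |
| Note 2, last sentence | Not a failure |

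No other section resolves this. Leaving such patients out of the denominator has little support, because 8.1 takes the proportion over the group.

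**2. Inputs for size.** From the document: n = 84 per arm (section 7.6). The protocol states no margin, error rate, expected success rate or interval method, so the 84 cannot be reproduced from it. Assumed for illustration only: the event counts, a 10-point margin, and the Newcombe or Wald two-sided 95% interval.

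**3. Effect per case.** 1/84 = 1.19 percentage points on that arm's rate.

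**4. Formulas.** Let p_T and p_C be the success proportions, d = p_T - p_C, and z = 1.96.

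- Newcombe lower limit: d - sqrt[(p_T - l_T)² + (u_C - p_C)²], where l_T and u_C are the Wilson lower limit for test and upper limit for control.
- Wald lower limit: d - z·sqrt[p_T(1 - p_T)/84 + p_C(1 - p_C)/84].

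Worked case: four active conversions in test, none in control, no other failures.

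- *Counted as successes:* 84/84 in both arms, d = 0, l_T = 95.63%, u_C = 100%. Newcombe: 0 - (100 - 95.63) = -4.37 points.
- *Counted as non-successes:* p_T = 80/84 = 95.24%, p_C = 100%, d = -4.76, l_T = 88.39%, u_C = 100%. Newcombe: -4.76 - (95.24 - 88.39) = -11.61 points. Wald: -4.76 - 1.96·sqrt(0.9524·0.0476/84) = -9.32 points.

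**5. Other counts.** Lower limits in points, Newcombe / Wald. The first row is also the result for every split when active conversions count as successes. The other rows count them as non-successes.

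| Active conversions, test vs control | No other failures | 2 other failures per arm |
|---|---|---|
| 0 vs 0, or all counted as successes | -4.37 / 0.00 | -6.14 / -4.61 |
| 1 vs 1 | -5.34 / -3.28 | -6.83 / -5.61 |
| 3 vs 0 | -9.98 / -7.54 | -11.01 / -9.59 |
| 4 vs 0 | -11.61 / -9.32 | -12.53 / -11.16 |
| 4 vs 1 | -10.49 / -8.68 | -11.50 / -10.36 |
| 4 vs 2 | -9.45 / -7.98 | -10.49 / -9.53 |
| 4 vs 4 | -7.44 / -6.44 | -8.49 / -7.79 |
| 0 vs 4 | -0.48 / 0.21 | -2.26 / -1.64 |

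**6. How often chance alone would do this.** Suppose each active conversion is equally likely to fall in either arm and there are no other failures. Counting them as non-successes then crosses the assumed 10-point margin with these probabilities:

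| Conversions in total | Newcombe | Wald |
|---|---|---|
| 4 | 4 vs 0: 1/16 = 6% | none: 0% |
| 5 | 5 vs 0 or 4 vs 1: 6/32 = 19% | 5 vs 0: 1/32 = 3% |
| 6 | 6 vs 0 or 5 vs 1: 7/64 = 11% | 7/64 = 11% |

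The figures do not rise steadily because the counts are discrete.

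**The case against.** The best reply is that Note 2 is the specific rule and Note 1 the general one. Note 2 exempts active conversion by name and the endpoint is binary, so these cases must be successes, and Note 1 merely lacks an exception clause. That is probably what was intended. But no sentence calls these cases successes, the rate is built from successes, and Note 1 defines success in terms they cannot meet. An analyst who applies Note 1 makes no error.

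The second reply is that few such cases should occur. Section 7.2 excludes previous operations at related sites, acute cholecystitis beyond 72 hours and gallbladder thickness above 10 mm, and section 8.3 requires experienced surgeons. The route is also narrow, since organ injury, unstoppable bleeding, difficult suturing and malfunction already count as failures. This stands as a limit on size: with no active conversions the two readings agree, and nothing in the protocol supports four to six of them.

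Third, the illustrations need lopsided splits, and the answer changes with the interval method. This also stands: with no other failures, 3 vs 0 and 4 vs 2 do not cross 10 points by either method. The calculations show that a changed conclusion is possible, not that it is likely.

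Fourth, section 5(4) is a summary and the case report form is not shown, so it is not established that the conversion reason goes unrecorded. That is fair. The recording point is an accompaniment to the fix, not a ground for the finding.

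The matter cannot simply be left to the SAP. The protocol has already fixed the definition, inconsistently, and a SAP that chose either reading would depart from one Note.

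**Conclusion.** The concern holds and must be fixed. Section 8.1 states contradictory rules for the same patients in the only primary endpoint of a non-inferiority trial. This follows from the text alone.

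The only part of the size that is certain is 1.19 points per active conversion at 84 per arm. Whether the choice would change the conclusion depends on the number of active conversions, their imbalance between arms, the other failures, the margin and the interval method, none of which the protocol gives. The severity therefore rests on the importance of the endpoint, not on the illustrative limits.

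**What to change.** Before any data are seen, amend section 8.1 so that each patient in its stated denominator has exactly one status. Either option removes the contradiction.

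- **Option A.** State that active conversions as described in 8.1(1) count as successes, and amend Note 1 accordingly. Cost: success no longer means completed with the assigned robot, and status rests on the operating surgeon's active/passive label.
- **Option B.** State that they count as non-successes, and amend the last sentence of Note 2. Its list of failure reasons should be brought into line too. Cost: slightly lower success rates and less precision. With no other failures, even one case per arm moves the Newcombe limit from -4.4 to -5.3, past a 5-point margin if that were the one used (Wald: 0.0 to -3.3, not past it). Four per arm move it to -7.4.

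Under either option, report the other classification as a named sensitivity analysis, tabulate conversions by reason and arm, and add conversion and its reason to the items in section 5(4), since Note 2 cannot be applied without the reason. The total cost is a wording change in the Notes, one extra analysis and one recorded item.

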7.3 Inclusion time

After signing the informed consent, subjects who meet the inclusion criteria and do not meet the exclusion criteria can be enrolled within 14 days. It is expected to take 12 months from the first case to the last case.

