7.5 The expected duration time of each subject

Each subject is observed up to 30 days after surgery, and efficacy and safety are evaluated at the end of the follow-up. So the expected duration of each subjects is 33 days. The additional 3 days are used for preoperative examination.

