7.6 Number of subjects required

In this clinical trial, 168 patients are enrolled, including 84 in the experimental group and 84 in the control group.

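### Hospital stay (8.2(9)) is counted from admission, so inpatient days before the operation enter an efficacy endpoint, adding variance and leaving a conditional route to bias

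*Protocol*

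**What the plan says.** Section 8.2(9) of the protocol gives hospital stay in days as "The total hospital days of subjects from admission to discharge". No separate postoperative stay is defined.

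Other parts of the protocol bear on this:

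- Section 5(5), which describes the period after surgery, states: "Time to first flatus, postoperative complications and hospital stay are recorded".
- Section 8.2(6) starts the clock for flatus when surgery finishes: "The time from the end of the operation to the subject's first flatus after surgery". Section 9.1(2) starts its adverse-event window at the same moment and closes it at discharge.
- Section 7.5 gives each subject 33 days, 30 of them after surgery: "The additional 3 days are used for preoperative examination". It does not say whether those 3 days are spent in hospital.
- Section 5(3) places allocation before the operation: "Qualified subjects are divided into the experimental group and the control group by randomized number given in an envelope". No interval from allocation to surgery is fixed.
- Section 6 assigns a different machine to each arm, MicroHand S in one and da Vinci in the other.
- Section 7.6 sets the size: "168 patients are enrolled, including 84 in the experimental group and 84 in the control group".

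**The concern.** Hospital stay is listed under efficacy and recorded with recovery measures, so a reader will take a difference between arms as a difference in recovery after the two procedures. With the clock started at admission, the value also contains time the device cannot affect. Two subjects with the same recovery get different values if one was admitted urgently with acute cholecystitis and worked up in hospital, and the other came in the day before an elective operation.

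Two things are at stake. The first is precision: variation in preoperative days widens the interval around the arm difference. The second is validity. Allocation precedes surgery and each arm needs its own robot, so an inpatient wait after allocation could differ by arm and would then appear as an effect of the device on hospital stay.

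**Working it through.** **Stated figure.** The protocol gives no standard deviation, expected difference, margin or power for hospital stay, so there is no figure to reproduce. Only the 84 per arm (7.6) comes from the document. All SDs and waits below are assumptions.

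**Decomposition.** Ignoring the hours of the operation itself, write total stay as T = A + B + P:

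- A: inpatient days before allocation
- B: inpatient days from allocation to the operation
- P: days from the end of the operation to discharge

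The expected arm difference in T is the sum of the expected differences in A, B and P. Randomisation makes the first zero on average. It does not do so for B, which arises after allocation. If B is also balanced, the expected difference in T equals that in P: nothing shrinks, and only precision is lost.

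**Loss of precision.** Take the preoperative part (A + B) as independent of P, and let k = SD_pre / SD_post. Then SD_total = sqrt(SD_post² + SD_pre²), and the standard error is multiplied by sqrt(1 + k²):

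- k = 0.5: sqrt(1.25) = 1.118, a rise of 12%
- k = 1: sqrt(2) = 1.414, a rise of 41%

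With 84 per arm, SE = SD_total × sqrt(2/84). The table shows the half-width of the 95% interval (1.96 × SE) and the power to detect a true 1-day difference in P at two-sided 5%.

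| SD_post (assumed) | SD_pre (assumed) | SD_total | Half-width, days | Power |
|---|---|---|---|---|
| 2.0 | 0 | 2.00 | 0.60 | 0.90 |
| 2.0 | 1 | 2.24 | 0.68 | 0.83 |
| 2.0 | 2 | 2.83 | 0.86 | 0.63 |
| 1.5 | 0 | 1.50 | 0.45 | 0.99 |
| 1.5 | 1 | 1.80 | 0.55 | 0.95 |
| 1.5 | 2 | 2.50 | 0.76 | 0.74 |

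The rows with SD_pre = 0 are what postoperative stay would give. They also show the case in which every subject spends the same number of days in hospital before surgery: a constant adds no variance.

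**Bias, if the wait differs.** If the mean of B differs between arms by w days, the estimated difference in T moves by w days. With no true difference in P, the chance that a two-sided 5% test declares one is Φ(w/SE − 1.96) + Φ(−w/SE − 1.96). For example, SD_post 2.0 and SD_pre 1 give SE = 2.24 × sqrt(2/84) = 0.345, and w = 0.5 gives 0.305. Over SD_post 1.5 to 2.0 and SD_pre 1 to 2:

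- w = 0.5 day: 0.21 to 0.44
- w = 1 day: 0.63 to 0.95

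These figures show how sensitive the endpoint is to a difference in waiting. They are not evidence that one exists.

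**The case against.** The definition is clear, reproducible and matches its name. Total stay is a legitimate resource measure, and the protocol's background section motivates the new device partly by cost. Section 5(5) lists what is recorded and does not redefine stay as postoperative; flatus after surgery could hardly start anywhere else. All of this stands. There is no contradiction in the text, only a choice of clock that suits a resource measure better than an efficacy measure.

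The bias route is also unproven. Section 5 puts the work-up in item (2), before allocation in item (3), and item (3) then runs from allocation through system check and anaesthesia to surgery. Nothing there suggests a long inpatient wait after allocation, and the protocol says nothing on robot availability. This stands too, so the bias can be stated only conditionally. It is not excluded, because the interval is left open.

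Three stronger readings are tempting but unsupported:

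- A reader might infer that the extra noise favours a non-inferiority claim. With balanced preoperative days the mean difference is unchanged and its interval is wider, which makes a margin-based claim harder. Noise would help only if a non-significant test were read as equivalence, and the protocol does not say that it will be.
- A reader might take section 7.3, under which "subjects who meet the inclusion criteria and do not meet the exclusion criteria can be enrolled within 14 days", as evidence of inpatient waiting. That window runs from consent to enrolment, and nothing places the subject in hospital during it.
- A reader might treat the 3 days in 7.5 as inpatient days that vary. They are not stated to be inpatient, and the same 3 days are budgeted for everyone.

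**Conclusion.** The point holds as a modest weakness of definition. An efficacy outcome includes any preoperative inpatient days, while two neighbouring measures start their clocks when the operation ends. The certain consequence, wherever preoperative stay varies, is lost precision: 12% on the standard error at k = 0.5 and 41% at k = 1, assuming independence and illustrative SD ratios. The possible consequence is a bias equal to any arm difference in inpatient wait between allocation and surgery; the protocol neither shows nor rules out such a difference. Priority is low to moderate, because this is one of nine secondary outcomes and neither the primary outcome in 8.1 nor the safety evaluation in section 9 depends on it.

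**What to change.** - In 8.2(9), define the efficacy measure as postoperative hospital stay, starting when the operation ends (the same start as time to first flatus) and stopping at discharge.
- Keep admission-to-discharge stay as a descriptive resource measure.
- Report the allocation-to-surgery interval by arm, so that a difference in waiting would be visible.

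The text change is about one sentence. Admission and discharge dates are already needed for the present definition, and the end of the operation is already needed for time to first flatus. The interval by arm also needs the allocation date. The cost is that total bed-days become descriptive. A subject allocated but not operated on would have no postoperative stay, so the new definition should say how such a case is handled.
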